6.4.3. Blinding of the Sponsor

Sponsor staff will be blinded to participants' assigned study intervention during the DB treatment period in Part 1 of the study, until all applicable participants had completed their Week 16 visit. The Sponsor study team will be unblinded to treatment assignment for the first 16 weeks of Part 1 (DB period) once treatment assignments are released for the IA.

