5. GENERAL METHODOLOGY AND CONVENTIONS

For Part 1, there will be a total of 2 planned analyses. The first (interim) analysis (IA) for Part 1 will be conducted when all applicable participants have completed or discontinued from study prior to their Part 1 DB Week 16 visit. The IA will be performed by the Sponsor and it will include all efficacy and safety data through Week 16. Data summaries from the IA will be shared with the study team. The study team will review the data in the context of the overall benefit-risk profile of etrasimod for the treatment of moderate-to-severe AD with prior systemic failure. The efficacy and safety data up to Week 16 will be utilized to assess the primary efficacy endpoint, secondary efficacy endpoints, and safety endpoints (Section 2.2, Section 5.1) and to make a go/no-go decision for initiating Part 2 of the study, as well as for completing the 52-week treatment for the Part 1 participants in the OLE. The IA efficacy results through Week 16 for Part 1 DB phase is not final and definitive.

The second (final) analysis for Part 1 will be conducted when all applicable participants have completed or discontinued from study prior to their Week 68 visit (including safety follow-up visits at Weeks 70 and 72) if Part 1 OLE is planned for completion by the sponsor. Otherwise, if Part 1 OLE is decided to be terminated by the sponsor, the final analysis will only be conducted based on data collected up to the date of study termination. The final analysis will contain final safety and efficacy data, as Part 1 final database, to assess the primary endpoints, secondary endpoints as well as exploratory efficacy endpoints (Section 2.2). This will also include efficacy analyses for Part 1 DB phase repeated based on this final data, and this final analysis is considered final and definitive.

For Part 2, there will only be one final analysis when all applicable participants have completed their Part 2 OL Safety phase Week 52 visit (including safety follow-up visits at Weeks 54 and 56) if Part 2 OL Safety phase is planned by the sponsor based on the Part 1 DB IA result. The final analysis will contain final safety data to assess the primary safety endpoints, and final efficacy data to assess exploratory efficacy endpoints (Section 2.2).

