7. INTERIM ANALYSES

An interim analysis (IA) will be conducted by the Sponsor in an unblinded manner to assess efficacy and safety after all applicable Part 1 participants complete or discontinue from study prior to the 16-week DB treatment period. The IA results will be used for decisions regarding stopping for futility and internal program development. Study conduct, including Part 1 participant continuation in OLE, will continue while the data are prepared and analyzed for the IA. The Part 2 enrollment will not be triggered until after IA shows an acceptable safety and efficacy of etrasimod 2 mg QD in the target population. Based on the IA results, the study may continue, or the study may be terminated early.

Specifically, the scope of this IA includes the following. When all applicable Part 1 participants have completed the 16-week DB treatment phase, an interim datacut will be performed that will include all efficacy and safety data up to Week 16 visit. After data cleaning is performed, unblinding of Part 1 DB treatment assignments will take place, and interim database will be released for the IA to be performed by the Sponsor and the study team. Investigators and other site staff will remain blinded during the OLE to participants' treatment assignment received in the Part 1 DB phase until the end of Part 1 OLE. Efficacy data summary will include the assessment of primary efficacy endpoint, secondary efficacy endpoints, and exploratory efficacy endpoints for Part 1 DB (Section 2.2) using the prespecified statistical methodologies (Section 5) to perform all relevant analyses described for Part 1 DB including subgroup analysis (Section 6.3). Safety data summary will include the assessment of all relevant safety endpoints (Section 3.5) descriptively summarized up to end of Part 1 DB phase.

Prior to this formal Part 1 DB IA, Sponsor may perform earlier unblinded interim analyses to inform internal decision-making regarding the development program. These earlier interim analyses will be conducted and reviewed by a limited number of team members independent of the study team. Details on these earlier unblinded interim analyses will be described in an unblinding operational plan.

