When Part 1 OLE treatment phase is completed, the final analysis will be performed based on the final released official database for Part 1 of this study. This final analysis of Part 1 will include repeating the IA for Part 1 DB phase using this final data, as well as cumulative analyses including the final data from the Part 1 OLE phase. There will be no IA planned for Part 2 OL Safety phase of this study. When Part 2 OL Safety treatment phase is completed, the final analysis will be performed based on the final released official database for Part 2 of this study.

The e-DMC will be responsible for ongoing monitoring of the safety of participants in the study according to the charter. The recommendations made by the e-DMC to alter the conduct of the study will be forwarded to Pfizer for final decision. Information about the e-DMC can be found in the e-DMC Charter, which outlines the operating procedures of the

committee, including specific description of the scope of their responsibilities, including a plan where communication timelines are defined.

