Appendix 4. Initiation of Prohibited Medications

The intercurrent event of initiation of prohibited medications will be identified using the final reconciliated PIPD dataset. The PD category of "concomitant medications" and the subcategory of "took prohibited concomitant medication/vaccine – meeting intercurrent event" will be used to identify this protocol deviation as the intercurrent event. This protocol deviation has to be verified using participant's entries of concomitant medications via clinical review. Once verified, the analysis population exclusion (APE) status will be checked "Yes" and this protocol deviation is deemed to be the intercurrent event of initiation of prohibited medications. The onset date of the protocol deviation as recorded on the PIPD dataset will DMB02-GSOP-RF02 7.0 Statistical Analysis Plan Template 31-Jan-2022

serve as the date of initiation of prohibited medications. This is applicable to the Part 1 DB phase only.

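### The definitive double-blind analysis is rerun after sponsor unblinding, with the prohibited-medication flag and the Week 16 window allocation not frozen beforehand

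*SAP*

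**What the plan says.** **Which run counts.** SAP Section 5 plans two analyses of Part 1. The IA is run once every participant has reached Week 16 or left before it, and it uses all efficacy and safety data to that visit. Even so, the SAP states: "The IA efficacy results through Week 16 for Part 1 DB phase is not final and definitive". The second analysis follows Week 68 and the follow-up visits to Week 72, or the date of termination if the OLE is stopped. It repeats the double-blind efficacy analyses, and "this final analysis is considered final and definitive". SAP Section 7 agrees: "This final analysis of Part 1 will include repeating the IA for Part 1 DB phase using this final data".

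**Who is unblinded, and when.** SAP Section 7 says: "After data cleaning is performed, unblinding of Part 1 DB treatment assignments will take place". The sponsor and study team then perform the IA. Protocol 6.4.3 is consistent with this: "The Sponsor study team will be unblinded to treatment assignment for the first 16 weeks of Part 1", once assignments are released for the IA. Against that, the OLE paragraph of Protocol 4.1 keeps the sponsor study team blinded to double-blind treatment, and Protocol 10.10 describes the sponsor's study medical monitor as a blinded team member. Neither gives an end date.

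**How the flag is set.** Under SAP Appendix 4 the prohibited-medication intercurrent event "will be identified using the final reconciliated PIPD dataset". A deviation in the relevant subcategory is verified against concomitant-medication entries by clinical review, given an analysis-population-exclusion status, and dated from that dataset. No reviewer, blinding requirement or lock date appears. Appendix 3 instead takes the date of the earlier event from the CRF, and keeps data up to two days after it.

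**How the Week 16 value is chosen.** SAP Appendix 2.1 uses the observation closest to the target day, with ties going to the later one. For anyone who leaves the study before the Week 68 window, it uses the latest observation in each earlier window.

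**The concern.** The Week 16 data are complete at the IA, so nothing scientific requires the governing estimate to wait. Waiting puts about a year between unblinding and the run that counts: 68 − 16 = 52 weeks of OLE, or 72 − 16 = 56 weeks with follow-up. During that time one input to responder status remains open to clinical judgement, and the sponsor study team knows both the assignments and the interim result.

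The window rule is a second and separate route. It needs no judgement and no data correction: a participant's departure after the IA is enough to swap one Week 16 value for another. Departures are also not independent of outcome. Protocol 7.1.5 takes participants who miss EASI-50 at Week 32 off treatment and through early termination and two follow-up visits. If the sponsor stops the OLE on the IA result, a literal reading applies the latest-observation rule to everyone still on study.

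At stake are the credibility of the primary estimate and the ability to show that any change between the two runs was not influenced by knowledge of arm.

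**Working it through.** **Inputs from the documents.** 30 per arm, assumed response 9% and 39%, 2-sided 95% interval with half-width 20.2 points (Protocol 9.5). Normal-approximation interval and stratified (CMH) formula (SAP 5.2.1.1). An intercurrent event makes the participant a non-responder under Estimand E1 (SAP 2.2.1), and a missing response also counts as non-response (SAP 5.3).

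**Assumptions.** Responder counts of 12 v 3 (39% and 9% of 30 are 11.7 and 2.7) and, for a smaller effect, 9 v 3. For the stratified check, 15 per arm in each IGA stratum. The documents give no intercurrent-event rate.

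**1. Reproduce the planned precision.**
1.96 × √(0.09 × 0.91/30 + 0.39 × 0.61/30) = 1.96 × √0.01066 = 20.2 points. The plan's figure is confirmed.

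**2. Leverage of one flag.** A reclassification changes the estimate only if the participant is otherwise an observed Week 16 responder, because everyone else already counts as a failure. For such a participant, the arm's rate and the difference move by 1/30 = 3.3 points, and 3.3/20.2 is about one sixth of the half-width.

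**3. Effect on the interval.**

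| Responders, etrasimod v placebo (of 30) | Difference | 95% CI |
|---|---|---|
| 12 v 3 | 30.0 | 9.4 to 50.6 |
| 11 v 3 (one etrasimod flag added) | 26.7 | 6.4 to 47.0 |
| 12 v 2 (one placebo flag added) | 33.3 | 13.7 to 53.0 |
| 9 v 3 | 20.0 | 0.4 to 39.6 |
| 8 v 3 (one etrasimod flag added) | 16.7 | −2.5 to 35.8 |

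For 9 v 3, √(0.3 × 0.7/30 + 0.1 × 0.9/30) = 0.100, so the half-width is 19.6. For 8 v 3 the same formula gives 19.1. The stratified formula gives nearly the same: 0.5 to 39.5 becomes −2.3 to 35.6.

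**4. The window rule.** The Week 16 window runs from Day 99 to the treatment switch day, or to Day 126 if that is earlier, with target Day 113. Suppose, purely as an illustration, an unscheduled assessment on Day 110 and the Week 16 visit and switch on Day 118. The distances from target are 113 − 110 = 3 and 118 − 113 = 5 days. While the participant is on study, the Day 110 value is used. If the participant leaves the study during the OLE, the Day 118 value replaces it. The rule matters only for participants with two or more observations in the window.

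**5. Is either input frozen before unblinding?** SAP Section 4 settles analysis-set membership before unblinding. An E1 flag does not remove anyone from the full analysis set; it changes that person's outcome within it. SAP Section 7 puts cleaning before unblinding for the IA, but does not say that the cleaned flags or allocations carry forward to the rerun.

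**The case against.** The strongest case on the other side has several parts.

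- **Flags probably exist before unblinding.** The IA runs the E1 analysis, which needs them, and cleaning comes first. This stands, and it narrows the gap to later edits. It does not close it, because the governing run uses the final dataset.
- **Section 4 may cover the flag through its analysis-population-exclusion label.** The SAP does not make that link, and set membership is not what the flag alters under E1.
- **Raters stay blinded.** Investigators, site staff and participants do not learn double-blind assignment until the OLE ends. This stands: the IGA scores themselves are not in question.
- **Checks exist.** Estimand E1a ignores intercurrent events, SAP Table 4 counts non-responders by event type and arm, and all deviations are listed. These are useful but partial. E1a is supportive only, and its data pass through the same window rule.
- **The SAP states in advance which result governs.** This stands. Having two runs is not in itself a defect, and a locked run would leave later-found errors in the headline estimate.

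A reader might also infer that the unblinded study team sets the flags. Protocol 10.1.7 gives data management to the sponsor or a designee, and Protocol 10.8.1 has the study team notified of prohibited medication, but Appendix 4 names no owner and a blinded designee is possible. Nor are both intercurrent events shown to be matters of judgement: no clinical-review step is described for treatment discontinuation. Nor is the Week 16 window a discretionary choice: Appendix 2.1 fixes it by algorithm, and the flaw is only that the algorithm depends on events after the double-blind period.

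**Conclusion.** The point holds in limited form. The definitive double-blind analysis follows sponsor unblinding. One of its inputs, the prohibited-medication flag, rests on clinical review without a specified lock or blinded reviewer. A second input, the Week 16 observation, can change because of OLE departures. The documents show the possibility of later change, not that it will happen or that any particular group would make it.

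The size is 3.3 points per otherwise-observed responder reclassified. A shift of 2/30 = 6.7 points would need two such participants whose changes push the difference the same way, so it should not be read as the expected effect. A single flag can move a borderline lower limit across zero, but only under the assumed smaller effect of 9 v 3. How many participants are exposed through either route is unknown.

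A reader might see a type I error problem here. The documents do not support that: SAP 5.1 and Protocol 9.1 state no hypotheses, although p-values will be produced. The risk is bias and loss of credibility in an estimate that will inform development decisions.

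**What to change.** Amend SAP Sections 5 and 7 and Appendices 2.1, 3 and 4 as follows.

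1. Before the IA unblinding, lock and sign off the double-blind data to Week 16, the prohibited-medication deviation coding, the intercurrent-event flags and dates, and the Week 16 window allocation. Name reviewers blinded to arm for the flags, and one source for the event date.
2. Make the latest-observation rule for double-blind windows depend only on discontinuation during the double-blind period.
3. Use the locked inputs for the definitive double-blind analysis. Report any later correction in a sensitivity rerun that lists every changed value with its reason.
4. Reconcile Protocol 4.1 and 10.10 with Protocol 6.4.3 and SAP Section 7 on who in the sponsor team is unblinded after the IA.

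The cost is SAP wording, a short protocol clarification and a documented freeze at a point where cleaning is already planned. The trade-off is that errors found later appear in the sensitivity rerun and not in the headline estimate. No sample size or precision figure changes.

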5.1. Hypotheses and Decision Rules

This protocol is designed to estimate the treatment difference in response rates of etrasimod 2 mg QD versus placebo, as well as their individual response rates (Section 5.2.1.1), for the treatment of moderate-to-severe AD based on the primary endpoint of IGA response rate at Week 16 in Part 1 DB (based on Estimand E1 as primary estimand) among adult participants (with baseline IGA \geq 2) with a history of a prior systemic therapy failure. There are no statistical hypotheses in this study, therefore no multiplicity adjustment will be made in this study.

5.2. General Methods

In Part 1 DB, as all participants randomized to treatment groups of etrasimod 2 mg QD and placebo will switch to open-label treatment of etrasimod 2 mg QD at Week 16, the treatment labels used for reporting DB visits up to Week 16 will be "Etrasimod 2 mg QD" and "Placebo" respectively. At the end of Part 1 OLE, when reporting OLE visits from Week 20 through Week 68, the treatment labels used will be "Etrasimod 2 mg QD" and "Placebo → Etrasimod 2 mg QD" respectively to differentiate these two treatment groups.

For Part 1 DB analyses up to Week 16, the following treatment comparison will be made at each timepoint, where applicable:

• Etrasimod 2 mg QD vs. Placebo.

The primary efficacy comparison for the primary endpoint of IGA response at Week 16 will be between etrasimod 2 mg QD and placebo. For analyses after Week 16 from Week 20 through Week 68 (Part 1 OLE phase), the following treatment comparison will be made at each timepoint,

• Etrasimod 2 mg QD vs. Placebo \rightarrow Etrasimod 2 mg QD.

For Part 2 OL Safety phase, there will only be one treatment group of etrasimod 2 mg QD, the label will be "Etrasimod 2 mg QD". There is no treatment comparison in Part 2. There will be no pooling of efficacy and safety data of Part 1 and Part 2 in this study.

Descriptive Summaries

In general, the data for all continuous endpoints will be summarized by treatment group and by timepoint in tables containing descriptive statistics (N as the number of participants evaluable for the endpoint at the timepoint, mean, standard deviation, standard error of the mean, minimum, 1^{st} , 2^{nd} (ie, median) and 3^{rd} quartiles and maximum) for actual and change from baseline (or percent change from baseline) values for those endpoints measured at baseline. In case when N=1 (ie, only one participant is available/evaluable for summary), standard deviation and standard error will be reported as "NA" (not applicable) while the remaining statistical parameters will have the same value as the mean. The data for all response-type binary endpoints will be summarized by treatment group and by timepoint in tables showing descriptive statistics: N, n (ie, number of responders), response rate, standard error (SE) of the response rate, and 95% confidence interval (CI) based on normal approximation, all expressed in %. If \hat{p} is the estimated response rate, then the 95% CI is calculated as:

$$\hat{p} \pm z_{0.975} SE = \hat{p} \pm z_{0.975} \sqrt{\frac{\hat{p}(1-\hat{p})}{N}}$$

where $z_{0.975}$ is the 97.5th percentile of the standard normal distribution and N is the number of participants evaluable for the endpoint at the timepoint. If the lower bound is calculated to be negative, it will be set to 0%; if the upper bound is calculated to be larger than 100%, it will be set to 100%. In case when response rate is 0 or 100%, standard error will be reported as "NA" and the 95% CI bounds will be the same as the response rate. The displays described above for continuous and response-type binary endpoints will only use available data with no imputation. Therefore, the calculation of response rates will use the number of evaluable participants as denominators.

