In Part 1 OLE phase, since no estimands are defined for (binary or continuous) efficacy endpoints, all observed data collected/assessed regardless of any prior intercurrent events will be included in deriving the efficacy endpoints at a visit. If the binary efficacy endpoint at any visit has missing value, it will be handled by setting the binary efficacy endpoint to non-response. This method of handling missing binary efficacy endpoint is known as missing response as non-response (MR=NR), which is similar to using Estimand E1a (treatment policy estimand). If the continuous efficacy endpoint at any visit has missing, it will remain as missing, without imputation of missing value at this visit, which is similar to using Estimand E2a (treatment policy estimand). The same approach of including all observed data collected/assessed regardless of any prior intercurrent events will also be applicable to Part 2 OL Safety phase. Missing binary efficacy endpoints in Part 2 OL Safety phase will not be imputed as non-response, only observed values will be summarized.

In general, missing values in any (binary or continuous) efficacy endpoint will not be imputed when summarizing these endpoints using descriptive statistics. In addition, missing values for safety endpoints will not be imputed.

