6. ANALYSES AND SUMMARIES

6.1. Primary Endpoint

6.1.1. Primary Analysis

The IGA response at Week 16 is the primary efficacy endpoint in Part 1 DB phase. The analysis of the primary endpoint will be based on Estimand E1 accounting for the intercurrent events using the FAS analyzed for participants with baseline IGA ≥2 (Section 4.1, Appendix 3). This corresponds to the primary estimand including only the preintercurrent-event data (Appendix 3). For the primary analysis, the normal approximation for the difference in binomial proportions adjusting for the actual stratification factor of baseline IGA (3 vs 4) via the CMH approach (Section 5.2.1.1) will be used. The baseline IGA from

the clinical database will be used as the actual stratification factor (Section 3.4.1). This CMH approach will be used to estimate the treatment difference in response rates of etrasimod 2 mg QD versus placebo and to generate 95% CI for the IGA response rate difference at Week 16 along with the 2-sided p-value (Section 5.2.1.1). Missing values will be handled by setting the IGA response value to non-response, MR=NR (Section 5.3). This is the primary analysis for IGA response at Week 16.

Analysis of IGA response at other visits prior to Week 16 (ie, exploratory endpoints) will also be analyzed using the same method based on the Estimand E1 including only the pre-intercurrent-event data on the FAS analyzed for participants with baseline IGA \geq 2.

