6.1.2. Supportive Analysis

A supportive analysis will be conducted for the primary efficacy endpoint of IGA response at Week 16 based on Estimand E1a without regard to intercurrent events using the FAS analyzed for participants with baseline IGA ≥2 (Section 2.2.3, Appendix 3). This corresponds to the supportive estimand including all data (Appendix 3). For this supportive analysis, the same normal approximation for the difference in binomial proportions adjusting for the actual stratification factor of baseline IGA (3 vs 4) via the CMH approach (Section 5.2.1.1) will be used. The baseline IGA from the clinical database will be used as the actual stratification factor (Section 3.4.1). This CMH approach will be used to support the primary analysis of estimating the treatment difference in response rates of etrasimod 2 mg QD versus placebo and to generate 95% CI for the IGA response rate difference at Week 16 along with the 2-sided p-value. Missing values will be handled by setting the IGA response value to non-response, MR=NR (Section 5.3). This is the first supportive analysis for IGA response at Week 16.

Supportive analysis of IGA response at other visits prior to Week 16 will also be performed using the same method based on the Estimand E1a including all data on the FAS, all analyzing participants with baseline IGA ≥ 2 .

When there are discrepancies between actual stratification factor (baseline IGA of 3 vs 4) versus reported stratification factor from the randomization system, a sensitivity analysis for the IGA response at Week 16 and visits prior to Week 16 will be conducted using the normal approximation for the difference in binomial proportions adjusting for the reported (instead of actual) stratification factor of baseline IGA of 3 vs 4 via the CMH approach (Section 5.2.1.1). This includes the pre-intercurrent-event data under Estimand E1 on the FAS analyzed for participants with baseline IGA ≥2 (Section 3.4.1, Section 4.1, Appendix 3).

In addition, for the primary endpoint of IGA response at Week 16 under Estimand E1, a summary similar to the following will also be generated to assess the impact of intercurrent events on the estimates.

Table 4. IGA Response at Week 16 and Intercurrent Events

*	Etrasimod 2 mg QD	nd E1, MR=NR Placebo	
	(FAS N=xxx) [1]	(FAS N=xxx) [1]	
n (%)	(ITISTV XXX)	(ITISTV XXX)	
IGA Responders	xx (xx.xx)	xx (xx.xx)	
IGA Non-Responders	xx (xx.xx)	xx (xx.xx)	

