1) Week 16 Completers with Observed Non-Response	xx (xx.xx)	xx (xx.xx)	
2) Week 16 Completers with Missing Response Set as Non-Response	xx (xx.xx)	xx (xx.xx)	
3) Initiation of Prohibited Medications Prior to Week 16 Visit (Earlier)	xx (xx.xx)	xx (xx.xx)	
4) Discontinued Study Treatment Due to Any Reason Prior to Week 16 Visit (Earlier)	xx (xx.xx)	xx (xx.xx)	
Reasons for Discontinuation of Study Treatment [2]			
Lack of Efficacy	xx (xx.xx)	xx (xx.xx)	
Adverse Event	xx (xx.xx)	xx (xx.xx)	
Death	xx (xx.xx)	xx (xx.xx)	
Lost to Follow-up	xx (xx.xx)	xx (xx.xx)	
Withdrawal by Subject	xx (xx.xx)	xx (xx.xx)	
Non-Compliance with Study Drug	xx (xx.xx)	xx (xx.xx)	
Protocol Deviation	xx (xx.xx)	xx (xx.xx)	
Pregnancy	xx (xx.xx)	xx (xx.xx)	
Physician Decision	xx (xx.xx)	xx (xx.xx)	
Medication Error without Associated Adverse	xx (xx.xx)	xx (xx.xx)	
Event			
Study Terminated by Sponsor	xx (xx.xx)	xx (xx.xx)	
Other	xx (xx.xx)	xx (xx.xx)	

^[1] N = number of participants in the FAS with Baseline IGA \geq 2. IGA response rates are calculated based on this as denominator.

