Appendix 3. Efficacy Data Set Descriptions For Part 1 Double-Blind Phase

There are two intercurrent events considered for Part 1 DB phase of this study, (1) the initiation of prohibited medications, and (2) the discontinuation of the study treatment (etrasimod 2 mg QD or placebo) due to any reason.

During the Part 1 DB phase, if a participant initiates prohibited medications (intercurrent event 1 above) and/or discontinues study treatment due to any reason (intercurrent event 2 above), the date of the earlier intercurrent event is noted (as recorded on relevant CRF page) and is used to differentiate and to define the data up to Week 16 into "Pre-intercurrent-event data", "Post-intercurrent-event data" (ie, both Pre- and Post-intercurrent-event data together), as laid out in the table below. Only efficacy data are in scope for this data differentiation.

Table 14. Efficacy Data Set Differentiation by Estimand in Part 1 DB Phase

Estimand	Participants who initiate prohibited medications and/or discontinue study treatment due to any reason prior to Week 16	Participants who do not experience any intercurrent events
E1	For this participant, the date/day of the earlier intercurrent event is flagged and noted (eg, Day X relative to baseline Day 1). Only data collected/assessed on or before Day X+2 (ie, allowing up to 2 additional days after date of earlier intercurrent event), as pre-intercurrent-event data, are included in this dataset. Any data collected/assessed after Day X+2, as post-intercurrent-event data, are excluded in this dataset. Visit windowing is performed after this data differentiation on the Pre-intercurrent-event data.	All data (unaffected due to no intercurrent events) of these participants will be included.
E1a	All data of these participants will be included regardless of the intercurrent events.	Same as E1 above.
E2	Same as E1 above.	Same as E1 above.
E2a	Same as E1a above.	Same as E1a/E1 above.
No Estimand	All data of these participants and available data will be inclu-	ded regardless of the intercurrent events.

All efficacy data collected in Part 1 OLE phase and Part 2 OL Safety phase will include all data collected/assessed regardless of these intercurrent events (ie, no estimand defined). All safety data will be analyzed regardless of these intercurrent events.

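### No 95% CI is planned for the per-arm Week 16 IGA response rate under Estimand E1; the only per-arm CI uses observed cases and has zero width at 0% or 100%

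*SAP*

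**What the plan says.** **The commitment.** The Synopsis and Protocol 9.5 define the Part 1 primary objective as estimating the Week 16 IGA response proportion with its 95% CI in each group, and the difference with its 95% CI. Protocol 9.1 repeats the arm rates as an objective. SAP 5.1, which bases the primary endpoint on Estimand E1, says the study estimates the difference "as well as their individual response rates (Section 5.2.1.1", so the reader is sent to the CMH section for the arm rates.

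**What is planned under E1.** SAP 5.2.1.1 gives an estimate, CI and p-value for the CMH-weighted difference only. SAP 6.1.1 applies missing-as-non-response and uses the CMH method "to generate 95% CI for the IGA response rate difference at Week 16 along with the 2-sided p-value". In SAP 6.1.2, "a summary similar to the following will also be generated to assess the impact of intercurrent events on the estimates". This is Table 4, with n (%) per arm on the FAS with baseline IGA of at least 2; its footnote says "IGA response rates are calculated based on this as denominator". The table shell has no CI.

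**The only per-arm CI.** Under Descriptive Summaries, SAP 5.2 defines a Wald interval for each arm and then says "The displays described above for continuous and response-type binary endpoints will only use available data with no imputation", with evaluable participants as the denominator. At 0% or 100%, "the 95% CI bounds will be the same as the response rate". SAP 5.3 repeats that "missing values in any (binary or continuous) efficacy endpoint will not be imputed when summarizing these endpoints using descriptive statistics".

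**The concern.** Part 1 tests no hypothesis, so the intervals are what the primary objective delivers. Under E1, a participant with an intercurrent event or no Week 16 value is a non-responder and stays in the denominator. The SAP 5.2 display applies neither rule. Followed literally, the SAP reports two Week 16 response rates per arm, and the only one with a CI is not the primary-estimand rate.

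The boundary rule is a second problem. An interval of 0 to 0% for zero responders claims certainty that 30 participants cannot give. The SAP recognises the boundary problem for the difference (it adds 0.5 to the responses and 1 to the denominator in the affected stratum) but has no equivalent for the arms.

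**Working it through.** **1. The plan's own precision.** Inputs from Protocol 9.5: n = 30 per arm, response 9% (placebo) and 39% (etrasimod), normal approximation, z = 1.96.

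- Placebo: 1.96 × √(0.09 × 0.91/30) = 10.24 points
- Etrasimod: 1.96 × √(0.39 × 0.61/30) = 17.45 points (stated: at most 17.5)
- Difference: 1.96 × √(0.09 × 0.91/30 + 0.39 × 0.61/30) = 20.24 points (stated: 20.2)

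The figures reproduce. They assume that all 30 participants are in each denominator, as under E1.

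**2. Which rate carries an interval.**

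| Place | Data rule | Denominator | Per-arm CI |
|---|---|---|---|
| SAP 5.2.1.1, 6.1.1 | E1, missing = non-response | FAS, baseline IGA ≥2 | None; difference only |
| SAP Table 4 | E1, missing = non-response | FAS, baseline IGA ≥2 | None; n (%) only |
| SAP 5.2, 5.3 | Observed values, no imputation | Evaluable participants | Wald |

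SAP 5.2 does not name its Appendix 3 data set. The No Estimand row of Table 14 ("All data of these participants and available data will be" included whatever the intercurrent events) appears to be meant. On that reading, a participant with an intercurrent event can count as a responder, and one with no Week 16 value leaves the denominator. If the pre-intercurrent-event data were used instead, participants whose Week 16 value is excluded would leave the denominator. Neither is the E1 rate.

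**3. Effect of the denominator.** The documents give no dropout rate. Assume that a fraction q of an arm, from 5% to 20%, has no Week 16 value and that all of them are failures under E1. Then the displayed rate is p′ = p/(1 − q), the denominator is 30(1 − q), and the half-width is 1.96 × √(p′(1 − p′)/[30(1 − q)]).

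| E1 rate | q = 5% | q = 10% | q = 20% |
|---|---|---|---|
| 39% | 41.1% ± 18.1 | 43.3% ± 18.7 | 48.8% ± 20.0 |
| 9% | 9.5% ± 10.8 | 10.0% ± 11.3 | 11.25% ± 12.6 |

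In counts: 12/30 under E1 is 40.0% (Wald 22.5 to 57.5%). With three missing values the display gives 12/27 = 44.4% (25.7 to 63.2%).

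**4. The boundary.** For 0/30 the SAP gives 0 to 0%, both by its stated rule and because the Wald standard error √(0 × 1/30) is 0. The alternatives are:

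- Wilson upper limit: z²/(n + z²) = 3.84/33.84 = 11.4%
- Clopper-Pearson upper limit: 1 − 0.025^(1/30) = 11.6%

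The probability of 0/30 is 0.91³⁰ = 5.9% in the placebo arm at 9%, and 0.61³⁰ ≈ 3.6 × 10⁻⁷ in the etrasimod arm at 39%.

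**5. Exact coverage at n = 30.** This is the sum of the binomial probabilities over the counts whose interval contains the true rate. The 13.0% and 29.8% are the Phase 2b placebo and etrasimod rates in Protocol 2.3.2.

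| True rate | Wald | Wald, boundaries replaced | Wilson | Clopper-Pearson |
|---|---|---|---|---|
| 9% | 93.7% | 99.6% | 95.2% | 98.5% |
| 13% | 90.4% | 90.4% | 95.1% | 97.3% |
| 29.8% | 95.2% | 95.2% | 93.0% | 97.4% |
| 39% | 92.9% | 92.9% | 94.0% | 96.2% |

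At 9%, Wald misses at 0 responders and at 8 or more. Of its 6.3 points of non-coverage, 5.9 come from 0/30. Away from the boundary, neither Wald nor Wilson is better at every rate.

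**The case against.** The strongest reply is that the gap matters little. The formal objectives tables and the population-level summary of E1 name only the difference, and Protocol 9.3.2 likewise plans a CI only for the difference. That CI is fully specified, with a boundary correction. Table 4 prints the E1 count, percentage and denominator, so a reader can compute an interval. No go/no-go rule uses a per-arm CI. All of this is correct, and it limits the consequence. It does not supply the interval: Protocol 9.5 and the Synopsis state it as part of the primary objective, and the SAP 5.1 cross-reference does not lead to one.

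A second reply is that Table 7 lists nothing under No Estimand for binary endpoints in the double-blind phase, so the all-data reading of SAP 5.2 is uncertain. This is fair, although Table 7 lists analyses rather than descriptive displays. The point that an intercurrent-event participant may count as a responder is therefore conditional. The mismatch with E1 is not, because it holds on either reading.

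A third reply is that Wald is the protocol's stated planning basis, that its 93.7% coverage at 9% is tolerable, and that the SAP marks the boundary case by printing the standard error as NA. Away from 0% and 100% the choice of interval is indeed secondary. At the boundary the SAP still prints 0 to 0% as a 95% CI.

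**Conclusion.** The concern holds. As written, the E1 arm rates have no CI, and the per-arm CI that is produced belongs to a rate with different responder and denominator rules. The boundary rule gives an invalid interval, with 5.9% probability in the placebo arm at the planned rate and almost none in the etrasimod arm.

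The size of the denominator effect rests on the assumed 5 to 20% without a Week 16 value. On that assumption, a 39% E1 rate displays 2 to 10 points too high, and its half-width of 18.1 to 20.0 points exceeds the planned 17.5. The 0/30 result needs no such assumption. The primary difference, its CI and the sample size are not affected. The plan should be corrected, but the validity of the between-arm comparison is not in question.

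**What to change.** - **SAP 6.1.1 and Table 4:** state that the per-arm Week 16 IGA response rate is reported under E1, with missing as non-response, on the FAS with baseline IGA of at least 2, with a 95% CI. Add the CI as a row in Table 4.
- **SAP 5.1:** point the cross-reference to that text.
- **Interval:** use one that does not collapse at 0% or 100% (Wilson or Clopper-Pearson), at least at those values. Replacing Wald elsewhere is optional.
- **SAP 5.2:** replace the boundary rule with such an interval or with NA. Deleting the rule is not enough, because the Wald formula itself gives zero width there. Keep the observed-case tables as supplementary and name their Appendix 3 data set.
- **EASI-75:** the same treatment is optional, since the per-arm CI objective covers IGA response only.

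The cost is a few sentences, one table-shell row and a standard procedure option, with no change to sample size or data collection. The downsides are that displayed rates may be slightly lower than observed-case rates, the intervals are asymmetric, Wald with only its boundaries replaced is conservative at 9% (99.6%), and full Wilson covers less than Wald at 29.8% (93.0% against 95.2%). The change is best made before Part 1 is unblinded, so that results cannot influence which rate is presented.
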